6.3.1.1. Radical Prostatectomy

Patients will undergo RARP using the DaVinci® surgical system as per the standard of care in the NHS. The operating surgeon must have performed a minimum of 100 cases. The procedure will be performed in accordance with the LaserSAFE technique. It differs from standard RARP in that the initial insertion of the robotic camera port is through a modified incision using the Alexis Laparoscopic System® (Applied Medical, Rancho Santa Margarita, CA). Surgical dissection will be carried out in the standard technique according to surgeon preference. NS will be performed following an intrafascial plane on both sides, if an intrafascial plane cannot be achieved due to

technical difficulty interfascial or extrafascial dissection will be registered. Immediately after the prostate is free from all attachments the specimen is removed from the patient using the Alexis port. Whilst the analysis is taking place the robot will be re-docked and pneumoperitoneum established. The robotic instruments will be reinserted. The surgeon will proceed to fashion the urethra-vesical anastomosis and perform a pelvic lymphadenectomy (where indicated) whilst the LaserSAFE procedures are being performed.

6.3.1.2. Lasersafe Technique

The LaserSAFE procedure is performed using an FCM called the Histolog[®] scanner developed by Samantree[®] which can be placed within the operating room. Histolog Scanner, Histolog Viewer, and accessories will be used according to the Instructions for Use. No modification to the CE-Mark/UKCA-Mark/FDA 510k clearance approved intended use will be made. The Histolog[®] scanner produces digital images with high, micrometre-range resolution and enables the visualization of tissue microstructures down to the cellular level. The microscope can image an area of 48x36 mm in approximately 60 seconds. Its operating principle is based on non-ionizing, low-power optical radiation (Laser) with a wavelength of 488±5 nm, and it uses a point illumination conjugated with a pinhole in front of the detector to eliminate out-of-focus signals.

The protocol of image acquisition is as follows: the prostate is cleaned using damp gauze and completely submerged in a solution that contains a photoreactive agent Histolog Dip[®] for 10 seconds. The specimen is rinsed with 0.9% NaCl solution, placed on the Histolog[®] scanner and lightly compressed using a mouldable weight. An initial live view scan confirms adequate positioning and stability of the specimen to avoid movement artefacts. If the preliminary scan is deemed satisfactory, a high-resolution digital image is acquired and stored in the microscope hard drive. The prostate is rotated to image the contralateral side. Once both posterolateral surfaces are imaged the prostate is placed in a container and fixed with formalin. Image acquisition takes less than 5 minutes. A pathologist will interpret the images on site or remotely depending on site specific requirements and complete a reporting case report form. The findings will be communicated directly to the surgeon.

Nerve sparing decisions will be guided by the result of the LaserSAFE technique.

The presence of cancer cells at the surface margin of the specimen will constitute a positive margin. Detailed results including the length of positive margin in 2 dimensions and multifocality, will be collected and included in the results.

In the presence of a posterolateral PSM, the performance of secondary resection (SR) of the ipsilateral neurovascular bundle (NVB) will be made if any of the following are present:

- (1) Multiple areas of PSM where the sum of each maximum dimension is >3 mm
- (2) any single PSM area >3 mm in maximum dimension

The resection of the NVB has been shown to result in oncological outcomes equal to negative surgical margin had been achieved in the first place.

SR of the ipsilateral NVB is performed in the following way: all tissue from the cut edge of Denonvilliers' fascia medially, the pararectal fat laterally, the pedicle cranially, and just beyond the urethrovesical anastomosis (including the puboprostatic ligament and Walsh's pillar) caudally is removed en bloc. Secondarily resected tissue is sent for routine paraffin-embedded histological analysis and is not analysed as part of the intraoperative FCM.

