3.1. Primary Objective

- To establish the sensitivity of pathology led LaserSAFE image interpretation to guide nerve-sparing decisions during radical prostatectomy

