3.3. Outcome Measures/Endpoints

- Primary endpoint
 - Sensitivity of LaserSAFE to detect positive margins in the posterolateral area of the prostate of more than 3 mm
 - Sensitivity will be monitored across the trial when the first 150, 300 and 500 participants have been recruited.
 - If sensitivity decreases below 85%, trial methodology will be reviewed and if considered appropriate the trial will be stopped.
- Secondary endpoints
 - Define the cut-off point for triggering secondary resection based on the prevalence of residual prostate cancer in secondary resections.
 - Overall sensitivity, specificity, PPV and NPV of LaserSAFE compared to FFPE analysis for any length of PSM
 - Overall specificity, PPV and NPV of LaserSAFE compared to FFPE analysis for any PSM > 3 mm.
 - Rate of residual prostate cancer in secondary resections of the neurovascular bundle
 - Prevalence of PSM detected by paraffin analysis in the overall cohort.
 - Prevalence of PCa biochemical recurrence or salvage treatment within 12 months after surgery
 - Mean score for EPIC-26 urinary incontinence domain at baseline, 3 and 12 months after surgery
 - Mean score for EPIC-26 erectile function domain at baseline, 3 and 12 months after surgery

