9.6.2. Primary outcome analysis

The primary analysis will evaluate the sensitivity of LaserSAFE interpretation for detecting positive surgical margins greater than 3 mm in the posterolateral prostate, using FFPE histopathology as the reference standard.

Interim analyses of sensitivity will be conducted after recruitment of the first 50, 150, 300, and 500 participants. If the observed sensitivity falls below % at any interim analysis, the trial will be stopped for futility. The final analysis will be undertaken once the target sample size of 693 participants has been reached. Sensitivity will be reported with a two-sided 95% confidence interval, calculated using the Wilson score method. Indeterminate or missing LaserSAFE results will be considered non-diagnostic and classified as false negatives in the primary analysis.

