9.6.3. Secondary Outcome Analysis

1. Diagnostic accuracy metrics. Sensitivity, specificity, positive predictive value (PPV), and negative predictive value (NPV) of LaserSAFE image interpretation will be calculated with corresponding two-sided 95% confidence intervals. These will be reported in two ways:
 - a. For detection of any positive surgical margin (PSM), regardless of length, compared with FFPE analysis.
 - b. For detection of PSMs greater than 3 mm, compared with FFPE analysis.
Two-sided 95% confidence intervals will be calculated using the Wilson score method.
2. Descriptive outcomes. The following will be summarised using descriptive statistics (means, proportions, and 95% confidence intervals as appropriate):
 - a. Rate of residual prostate cancer in secondary resections of the neurovascular bundle.
 - b. Prevalence of PSMs detected by paraffin analysis in the overall cohort.
 - c. Prevalence of biochemical recurrence or salvage treatment for prostate cancer within 12 months post-surgery.
 - d. Mean scores for the EPIC-26 urinary incontinence and erectile function domains at baseline, 3 months, and 12 months post-surgery.

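### The protocol does not say which LaserSAFE reading counts as positive in the >3 mm accuracy table, and its only positivity definition (any cancer cells) does not fit that endpoint or the >3 mm resection rule

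*Protocol*

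**What the plan says.** The primary objective (Protocol 3.1) is tied to a decision: "To establish the sensitivity of pathology led LaserSAFE image interpretation to guide nerve-sparing decisions during radical prostatectomy". The primary endpoint (3.3, repeated in 9.1) is "Sensitivity of LaserSAFE to detect positive margins in the posterolateral area of the prostate of more than 3 mm". Section 9.6.2 analyses "sensitivity of LaserSAFE interpretation for detecting positive surgical margins greater than 3 mm in the posterolateral prostate, using FFPE histopathology as the reference standard". Section 9.6.3, item 1b, adds specificity, PPV and NPV "For detection of PSMs greater than 3 mm, compared with FFPE analysis", separately from the any-length metrics in item 1a.

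On the LaserSAFE side, section 6.3.1.2 says "The presence of cancer cells at the surface margin of the specimen will constitute a positive margin". Length is recorded but plays no part in that definition: "Detailed results including the length of positive margin in 2 dimensions and multifocality, will be collected and included in the results". The same section makes secondary resection depend on length, through either "any single PSM area >3 mm in maximum dimension" or "Multiple areas of PSM where the sum of each maximum dimension is >3 mm". Section 9.2 allows this resection cut-off to rise in 1 mm steps to 6 mm, while the endpoint stays at >3 mm.

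Sections 3.3 and 9.1 attach a review and possible stopping of the trial to sensitivity below 85%. The only false-negative scoring rule (9.6.2) covers indeterminate or missing LaserSAFE results.

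**The concern.** A sensitivity needs two definitions: what makes a side positive on the reference standard, and what makes it positive on the index test. The >3 mm wording settles the first. For the second, the protocol offers only the any-cancer definition, which is not the rule the surgeon acts on.

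If that definition fills the >3 mm table, three things follow.

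- A margin over 3 mm on FFPE that LaserSAFE sees but reads at 3 mm or less leads to no resection, yet it is a true positive. The 85% safeguard, meant to protect against missed significant margins, cannot see this error.
- A margin of 3 mm or less, read correctly and left alone under the rule, is a false positive in the >3 mm table. Specificity and PPV then fall short of 100% even for a perfect reader.
- If the resection cut-off rises, FFPE >3 mm margins that are read correctly but left in place by rule also count as successes, with no reading error at all.

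The primary estimate and the stopping safeguard therefore depend on a choice the protocol does not make.

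**Working it through.** **The plan's own figure.** Inputs from 9.3: sensitivity 0.91, half-width 0.05, 95% confidence, prevalence 0.20, 10% allowance.

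- n = 1.96² × 0.91 × 0.09 / 0.05² = 125.85, so 126 positives.
- 126 / 0.20 = 630, and 630 × 1.10 = 693.

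All three stated figures are reproduced. The point concerns scoring, not an error in the sample size.

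**Two scorings of the same case.** Each row is one side, with the 3 mm cut-off in force.

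| FFPE length | LaserSAFE reading | Resection triggered | Any-cancer scoring, >3 mm table | Length-based scoring, >3 mm table |
|---|---|---|---|---|
| 5 mm | 2 mm | no | true positive | false negative |
| 1 mm | 1 mm | no | false positive | true negative |

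**Sensitivity.** Let u be the share of LaserSAFE-detected FFPE >3 mm margins that LaserSAFE reads at 3 mm or less. The protocol gives no value, so u is an assumption. Sensitivity under length-based scoring is 0.91 × (1 − u).

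- u = 5%: 0.91 × 0.95 = 0.865
- u = 10%: 0.91 × 0.90 = 0.819
- u = 20%: 0.91 × 0.80 = 0.728
- Falls below 85% when u > 1 − 0.85/0.91 = 6.6%

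In whole counts, take 126 FFPE >3 mm margins with 115 detected at any length. Intervals are Wilson, as in 9.6.2.

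| Assumed u | Any-cancer scoring | Length-based scoring |
|---|---|---|
| 0% | 115/126 = 91.3% (85.0 to 95.1) | 115/126 = 91.3% (85.0 to 95.1) |
| 5% | 91.3% | 109/126 = 86.5% (79.5 to 91.4) |
| 10% | 91.3% | 104/126 = 82.5% (75.0 to 88.2) |
| 20% | 91.3% | 92/126 = 73.0% (64.7 to 80.0) |

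Eight undersized readings are enough to fall below the safeguard: 107/126 = 84.9%.

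**Specificity and PPV for a perfect reader.** Take 100 units, 20 with any PSM (the 20% of 9.3). Let s of those 20 be 3 mm or less; s is an assumption. Under any-cancer scoring, all 20 are LaserSAFE-positive, 20 − s are true positives and s are false positives.

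- Specificity = 80/(80 + s): 94.1%, 88.9%, 84.2% for s = 5, 10, 15
- PPV = (20 − s)/20: 75%, 50%, 25%

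If the reader also measures exactly on the FFPE scale, length-based scoring gives 100% for both.

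**What length-based scoring does to planning.** At ±5 points, sensitivity of 0.8645 (u = 5%) needs 180 positives, or 180/0.20 = 900 participants before inflation. At 0.819 (u = 10%) it needs 228, or 1,140. At the look after 150 participants, 20% prevalence gives 30 positives, and an observed value below 85% means 25 or fewer detected. The binomial probability of that is 13% if true sensitivity is 91% and 38% if it is 86.5%.

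**The case against.** The strongest reply is that the protocol never states the any-cancer scoring. The definition sits in the technique section and says what a positive margin is, not how to fill a 2×2 table. The statistical section keeps any-length and >3 mm analyses apart, and detecting margins of more than 3 mm can be read as requiring a LaserSAFE call above 3 mm. A reader might infer that the protocol has adopted a rule that scores undersized margins as true positives. The documents do not support that: they leave two readings open, and the definition they do state points to the less suitable one.

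A second reply is that cell-by-cell scoring belongs in the SAP. That would normally be enough. Here, however, the Study Summary only requires the definitive analysis plan before recruitment finishes, which could be after the looks at 50, 150, 300 and 500 participants. The scoring has to be fixed before a look that can stop the trial.

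A third reply is that undersizing should be uncommon. Section 2 says en-face margins appear larger than cross-sectional ones, and 6.3.1.2 uses maximum dimensions and sums foci. This stands: no rate is given, u may be small, and the sensitivity figures show a range, not an expected loss. It does not affect the specificity and PPV problem.

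Finally, any-cancer detection of FFPE-significant margins is a coherent quantity, since section 2 says no en-face threshold is established. That is a reason to report it alongside, not to leave the primary definition open. Nor is undersizing invisible in the data, because LaserSAFE lengths are collected; it is invisible to the 85% rule if any-cancer scoring is used.

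**Conclusion.** The concern holds as a gap and a mismatch. The only stated LaserSAFE positivity definition has no length, the primary endpoint and its safeguard are about margins over 3 mm, the decision in theatre depends on a LaserSAFE length over 3 mm, and no section connects them.

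If the definition is applied literally, specificity and PPV for >3 mm are understated even for a perfect reader, by an amount set by the assumed share of small margins. Sensitivity as a measure of correct decisions is overstated by an amount set by u, which is unknown and may be low; the 85% line is crossed at u = 6.6% if detection is 91%.

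A reader might also infer that fixing positivity at 3 mm cures the problem of larger margins left in place after the cut-off rises. It does not: those sides would still score as true positives, so they need their own count.

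This concerns scoring only. It takes no position on what the clinical resection cut-off should be.

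**What to change.** In 9.1, 9.6.2 and 9.6.3 item 1b, before the first interim look:

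1. Define LaserSAFE-positive, for every >3 mm metric and for the 85% monitoring, as a recorded reading that meets the 6.3.1.2 length criteria at 3 mm (single area, or sum of maximum dimensions). Apply this unchanged for scoring, whatever resection cut-off is in force.
2. Keep any-cancer positivity for the any-length metrics, and show any-cancer detection of FFPE >3 mm margins next to the primary result.
3. Report two separate counts: (a) FFPE >3 mm margins seen but read at 3 mm or less; (b) FFPE >3 mm margins read above 3 mm but left in place because the cut-off had risen.
4. Confirm that FFPE margin length is captured. Section 6.4.1 mentions only presence or absence of PSM on the case report form.

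No new LaserSAFE measurement is needed. The costs should be stated openly. Sensitivity may come out below the planned 91%, with a wider interval than ±5 points at the current size and more frequent 85% triggers. Because en-face lengths run larger, some margins of 3 mm or less on FFPE will read above 3 mm and score as false positives.

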6.3.1.3. LaserSAFE Image Analysis

Images stored in the confocal microscope will have a unique identifier for each patient and will be annotated to describe the side and orientation. These images will be interpreted by a pathologist with expertise in Uro-pathology and who have been trained in the interpretation of confocal images using an image databank with representative examples. A specially designed case report form (Figure 2) will be used to describe the findings.

6.3.1.4. Histolog Remote viewer

The Histolog Viewer is an image management software intended to access, display, annotate, manage, store and share collections of digital Histolog Scanner images and their associated metadata. I will allow pathologist to access the images obtained in the operating room in real time and provide a diagnosis on the margin status of a prostatectomy specimen. Results of the analysis will be communicated via telephone directly to the surgeon.

6.4. Subsequent Assessments and Procedures

6.4.1. Follow Up

Clinical follow-up will be performed according to each participating centre's standard procedures after RARP.

For study follow-up patients will receive a paper or electronic copy of the EPIC-26 questionnaire before RARP, at 3 and 12 months after surgery. The Expanded Prostate Cancer Index Composite (EPIC) is an instrument designed to evaluate quality of life after PCa treatment. The instrument was developed by the University of Michigan (28) and has been validated to be used as an electronic instrument (29). It assesses health-related quality of life across five domains relevant after diagnosis and treatment of PCa. It has 26 items grouped into 5 domains:

1. Urinary Incontinence (4 items)
2. Urinary Irritative/Obstructive (4 items)
3. Bowel (6 items)
4. Sexual (6 items)
5. Hormonal/Vitality (6 items)

[figure not shown]
Each item has a Likert-type response scale (e.g. "no problem" to "big problem"), scored 1–5. Items in each domain are averaged, then transformed linearly to a 0–100 scale. Interpretation relies on domain-specific means, with MIDs (4–12 points depending on domain) to guide whether changes are clinically meaningful.

FFPE reports of the radical prostatectomy specimen will be reviewed and reported in a case report form, the presence or absence of PSM will be documented.

PSA assessments will be performed according to the standard of care at each centre. Biochemical recurrence and the need for secondary treatments will be recorded at 12 months. Adverse events within 90 days of the surgery will be recorded according to the description below.

A schedule of all trial assessments and procedures is set out in Appendix 1.

6.4.2. Participant pathway diagram

6.5. Samples

6.5.1. Sample Storage

In the study, prostate specimens will be collected from patients in accordance with the patient consent form and patient information. The radical prostatectomy specimens and secondary resections will be appropriately sent to the pathology department of the participating institution for standard of care pathology assessment.

The participating pathology departments will process, store and dispose of surgical specimens, in accordance with all applicable legal and regulatory requirements, including the Human Tissue Act 2004 and any amendments thereto.

No samples will be stored for any additional analysis related to the procedures outlined in this study.

6.5.2. Sample Transfer

The surgical specimens will not be transferred to any party not identified in this protocol and are not to be processed and/or transferred other than in accordance with the patients' consent. After ethics approval for the study has expired, the prostatectomy specimens will be disposed of in accordance with the Human Tissue Act 2004 and any amendments thereto or transferred to a licensed tissue bank.

6.6. Discontinuation/Withdrawal of Participants

Participants may be withdrawn from the trial for the following reasons:

- Unable to undergo RARP as planned due to medical reasons
- Unable to perform nerve sparing RARP as planned due to anatomical/technical difficulty during surgery.
- Patient expresses desire to withdraw the consent to continue participating in the study.
- Patients' death

The decision to withdraw a participant from treatment will be recorded in the CRF and medical notes/electronic health record system. If a participant withdraws consent no additional data will be collected and if requested the participants information will be deleted from the study records.

6.7. Definition of End of Trial

The trial will close 12 months after the last surgery of the last participant when the final follow up data will be collected.

7. FINANCE AND SUPPLY OF EQUIPMENT

The research costs for the study will be supported by a collaborative research grant from SamanTree Medical SA. SamanTree will reimburse the participating centres in the Post-Market Registry to Collect Real-World Clinical Data on the Use of the Histolog® Scanner.

The Histolog Scanner and consumables has been purchased with the support of the UCLH Charity.

8. DATA MANAGEMENT

8.1. Confidentiality

The study is compliant with the requirements of the General Data Protection Regulation (2016/679) and the UK Data Protection Act (2018). All Investigators and study site staff will comply with the requirements of the General Data Protection Regulation (2016/679) with regards to the collection, storage, processing and disclosure of personal information, and will uphold the Act's core principles. UCL is the data controller, Data protection registration No Z6364106/2025/10/66; the UCL Data Protection Officer is [contact]. The data processors will be designated in the trial delegation log.

The study will be collecting the following identifiable personal data: Patients name, date of birth, height, weight, hospital number, email address extracted from the medical records. Any patient identifiable data will only be stored for consent purposes. After patient enrolment the anonymised patient ID assigned by RedCAP will be used on all trial records. This trial number will be known by all LaserSAFE study site staff. All clinical information including scans, biopsy results and blood results will be kept in trial records and analysed at the end of the trial. The records will be kept in a secure manner in the research offices with access available to named individuals from the trial group only. All imaging data will be held confidentially and processed by the named investigators for the purpose of image registration analysis. The paper records will be retained for a minimum of 20 years after the end of the trial, according to the local hospital's guidelines.

8.2. Data Collection Tools and Source Document Identification

Data will be collected from sites from source medical notes directly into the electronic CRFs developed in RedCAP. No copies of source data will be kept by the research team. The following clinical data will be collected for each patient by the CRF: Histology reports; clinical stage; Prostate Specific Antigen (PSA) (pre- and post-surgery); imaging (mpMRI, PSMA-PET/CT and bone scan); results and record of additional postoperative therapies.

The delegation log will identify all those personnel with responsibilities for data collection and handling, including those who have access to the trial database.

